#### Elimination

Apparent clearance (CL/F) is approximately 1000 L/h. The half-life of ibrutinib is 4 to 6 hours. Ibrutinib, mainly in the form of metabolites, is eliminated primarily via feces. After a single oral administration of radiolabeled [C]-ibrutinib in healthy subjects, approximately 90% of radioactivity was excreted within 168 hours, with the majority (80%) excreted in the feces and less than 10% accounted for in urine. Unchanged ibrutinib accounted for approximately 1% of the radiolabeled excretion product in feces and none in urine, with the remainder of the dose being metabolites.

#### **1.2.2 Clinical efficacy data**

Efficacy results from two separate studies demonstrate that ibrutinib has robust activity as a single-agent in the treatment of subjects with relapsed or refractory MCL. As of October 2011, 60 subjects with MCL (9 from study PCYC-04753 and 51 from study PCYC-1104-CA) had been evaluated for response to treatment with ibrutinib; despite the poor-risk nature of the MCL population on these 2 studies, the ORR was 70% (42/60); this is very favorable in comparison to historical data with bortezomib in a less heavily pretreated relapsed MCL population.

In the PCYC-04753 study (a phase I, multicenter, dose escalation study of 56 patients with a variety of B-cell malignancies) all 9 subjects with MCL were evaluable for response. Of these, 7 achieved an objective response by the Revised Response Criteria for Malignant Lymphoma [14], including 3 CRs and 4 PRs; in addition there was 1 SD and 1 PD. All of the subjects responding to treatment achieved response at the time of the first response assessment (after 2 cycles of treatment). Of the 3 subjects who achieved a CR, 2 subjects did so upon initial response assessment and 1 was a PR initially who converted to CR after 8 cycles (28-days cycle duration) of therapy. Responses have been durable; 5

Study Numbers: NU 14H06  
PCI-32765MCL2003Initial version: September 24, 2014  
AMD 11: ver. date 08.06.2022

subjects who entered a long-term follow-up study and continued to receive study treatment achieved duration of response ranging from 10.5 to 27.5 months from treatment initiation.

The safety and efficacy of ibrutinib in patients with MCL who have received at least one prior therapy were evaluated in an open-label, multi-center, single-arm trial of 111 previously treated patients. The median age was 68 years (range, 40 to 84 years), 77% were male, and 92% were Caucasian. At baseline, 89% of patients had a baseline ECOG performance status of 0 or 1. The median time since diagnosis was 42 months, and median number of prior treatments was 3 (range, 1 to 5 treatments), including 11% with prior stem cell transplant. At baseline, 39% of subjects had at least one tumor  $\geq 5$  cm, 49% had bone marrow involvement, and 54% had extranodal involvement at screening. Ibrutinib was administered orally at 560 mg once daily until disease progression or unacceptable toxicity. Tumor response was assessed according to the revised International Working Group (IWG) for non-Hodgkin's lymphoma (NHL) criteria. The primary endpoint in this study was investigator-assessed overall response rate (ORR). Efficacy results indicated an ORR of 65.8% (95% CI 56.2-74.5; 69% by IRC), including CR rate of 17.1% and PR rate of 1548.6%. The median DOR was 17.5 months, and median time to response 1.9 months.

### 1.2.3 Toxicity data

The data described below reflect exposure to ibrutinib in a clinical trial that included 111 patients with previously treated MCL treated with 560 mg daily with a median treatment duration of 8.3 months. The following risks are discussed in more detail in the full prescribing information:

- Hemorrhage (5%)
- Infections (25%)
- Myelosuppression (41%)
- Renal Toxicity (67%)
- Second Primary Malignancies (5%)

Because clinical trials are conducted under widely variable conditions, adverse event rates observed in clinical trials of a drug cannot be directly compared with rates of clinical trials of another drug and may not reflect the rates observed in practice.

The most commonly occurring adverse reactions ( $\geq 20\%$ ) were thrombocytopenia, diarrhea, neutropenia, anemia, fatigue, musculoskeletal pain, peripheral edema, upper respiratory tract infection, nausea, bruising, dyspnea, constipation, rash, abdominal pain, vomiting and decreased appetite. The most common Grade 3 or 4 non-hematological adverse reactions ( $\geq 5\%$ ) were pneumonia, abdominal pain, atrial fibrillation, diarrhea, fatigue, and skin infections.

An evaluation of the safety data across 5 clinical studies (sponsored by Pharmacyclics & Janssen Scientific Affairs) including 392 subjects found moderate toxicities associated with ibrutinib treatment. The most common ( $> 10\%$ ) treatment-emergent adverse events (AEs) were diarrhea

Study Numbers: NU 14H06  
PCI-32765MCL2003Initial version: September 24, 2014  
AMD 11: ver. date 08.06.2022

(40.4%), fatigue (32.1%), nausea (24.0%), cough (17.6%), and peripheral edema (16.7%). These AEs are classified as grade 1 or 2 in severity and were not dose-limiting. Grade 3 or 4 adverse events were noted in about 45.8% of the patients, which were typically hematologic in nature (anemia 5.8%, thrombocytopenia 5.1%, and neutropenia 4.5%). Serious adverse events (SAEs) were experienced by 35.9% of subjects, which included pneumonia (4.5%), febrile neutropenia (3.2%), and atrial fibrillation (2.9%).

Hemorrhagic AEs have been reported following ibrutinib treatment, either as monotherapy or in combination with other agents. Out of 392 subjects, 6 (1.5%) experienced subdural hematoma; in 5 of these 6 the event was reported as serious, and in 2 it was determined to be possibly related to ibrutinib. Additional serious hemorrhagic events have included hematuria (2 subjects), cerebrovascular accident with intracerebellar hemorrhage, GI hemorrhage, hematoma, and hemorrhagic enterocolitis (1 subject each). Non-serious bleeding events have included contusion, ecchymosis, petechiae, epistaxis, retinal hemorrhage, hematuria, hemoptysis, and hematochezia. These events have generally resolved.

Although in vitro studies have found that ibrutinib can inhibit platelet function, the clinical significance of this effect is not clear. An expert review of the hemorrhagic SAEs that have occurred in clinical studies seemed to conclude that the incidence of subdural hematoma was unlikely to be related to the platelet inhibitory activity of ibrutinib. Other potential risk factors for subdural hematoma may have included age, any history of fall, or concomitant use of anti-coagulants such as warfarin.

Across all ibrutinib studies—monotherapy and combination treatment—32 (8.2%) of the 392 subjects discontinued treatment due to an AE, including 12 for reasons related to infection or its complications (e.g., pneumonia, sepsis, bacteremia, pyrexia, neutropenia with or without fever, etc.).

Refer to the investigator's brochure for additional toxicity information.

### 1.3 Rationale for the Current Study

There is an unmet medical need for developing new therapeutic options to treat patients with MCL. Ibrutinib is currently the focus of several mono and combination-treatment studies, in a variety of B-cell malignancies. However, the role of single-agent ibrutinib in a maintenance therapy setting for previously-untreated MCL patients has not been explored. We therefore propose a phase II trial to assess the role of ibrutinib as maintenance therapy for MCL patients who have achieved response to induction with either R-Hyper-CVAD, R-CHOP (with or without cytarabine-containing cycles [1, 2]), or R-Bendamustine, with or without auto transplant. The study population would therefore involve patients with histologically confirmed MCL who have achieved either CR or PR after intensive induction systemic chemotherapy.

Ibrutinib will be given as maintenance therapy at a daily dose of 560 mg taken orally (1 cycle = 28 days). In the PCYC-1104-CA study, ibrutinib was administered to relapsed/refractory MCL patients as a fixed dosage of 560

Study Numbers: NU 14H06  
PCI-32765MCL2003Initial version: September 24, 2014  
AMD 11: ver. date 08.06.2022

mg/day; in this study, 96% of the patients retained steady-state ibrutinib AUC values >160 ng·h/mL, indicating that the vast majority of patients who received a dose of 560 mg/day achieved exposures yielding full BTK active-site occupancy. This dose in relapsed or refractory MCL patients showed an acceptable toxicity profile. Based on these data, the oral daily 560 mg dose has been selected for this study. Treatment will continue up to 4 years in the absence of progression of disease or intolerable toxicity, or patient preference. We also plan to collect whole blood samples from all patients in order to monitor MRD results by PCR; samples will be collected at four time-points: baseline (pre-treatment), after 1 month and 6 months of treatment, and approximately 18-24 months post-first dose of treatment.

## 2.0 STUDY OBJECTIVES & ENDPOINTS

### 2.1 Primary Objective & Endpoint

The primary objective will be to determine the progression-free survival (PFS) rate after 3 years.

Progression-free survival (PFS) will be defined as the absence of disease progression or death from any cause. The rate of PFS will be calculated after 3 years.

### 2.2 Secondary Objectives & Endpoints

Secondary objectives will include the following:

#### 2.2.1 Assess toxicity.

Adverse events will be defined according to the National Cancer Institute's Common Terminology Criteria for Adverse Events (NCI CTCAE) version 4.03. The occurrence and severity of each will be recorded.

#### 2.2.2 Determine rates of conversion from PR to CR.

The rate of conversion from PR to CR will be calculated based on Cheson 2007 criteria.

#### 2.2.3 Determine median overall survival (OS) after 4 years.

Patients will be evaluated monthly for the first 6 months on treatment, then every 3 months thereafter. Patients who go off treatment will continue to be followed for survival up to a maximum of 4 years post-first dose. Follow-up will occur every 3 months (up to 2 years after the first dose of treatment) and then every 6 months thereafter (up to 4 years post-first dose). Median OS after 4 years will be calculated.

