## STUDY SCHEMA

Patients must receive at least 4 cycles of induction chemotherapy with or without auto-SCT, including R-CHOP (with or without alternating R-DHAP), R-Hyper-CVAD, or R-bendamustine.

Per Cheson 2007 criteria.

During treatment, 1 cycle = 28 days. Patients will be evaluated (and drug will be dispensed) prior to each cycle for the first 6 months, then every 3 cycles thereafter for the remainder of treatment. See section 4.2 for the provision of 6-month visits after 2 years.

Follow-up schedule for patients off-treatment will be every 3 months up to 2 years post-first dose, then every 6 months up to 4 years post-first dose. Date of progression will be documented as well.

Study Numbers: NU 14H06  
PCI-32765MCL2003Initial version: September 24, 2014  
AMD 11: ver. date 08.06.2022**STUDY SUMMARY**

Title	A Phase II Clinical Trial Evaluating Ibrutinib Maintenance Following Intensive Induction for Patients with Previously Untreated Mantle Cell Lymphoma (MCL)
Version Date	August 8, 2022 (Amendment 11)
Phase/Design	Phase II, single-arm, multicenter, open-label study
Study Center(s)	Lead site: Northwestern University Participating sites: University of Michigan, University of Utah, and Dana Farber d/b/a Massachusetts General Hospital
Objectives	
Primary objective: Determine the 3-year PFS in patients with previously-untreated MCL who achieve response to intensive induction therapy and then receive maintenance Ibrutinib.
 
Secondary objectives:
 
 
• Toxicity
 
• Rates of conversion from PR to CR
 
• Median overall survival at 4 years
 
 
Exploratory objectives: Monitor MRD results by PCR and correlate with PFS and OS.

Sample Size	36 evaluable patients (patients who receive < 1 complete cycle of therapy will not be considered evaluable for efficacy endpoints and will be replaced; we estimate this to represent 3 or fewer subjects)

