#### 6.2.3 Median overall survival at 4 years

Overall survival (OS) will be defined as the duration of time from start of treatment up to 4 years from the start of study treatment.

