## **10.2 Sample Size and Power Calculations**

The primary endpoint is three-year PFS. Our null hypothesis is that ibrutinib maintenance will yield no improvement upon the 60% three-year PFS observed in

studies described above. We consider an observed three-year PFS of 80% both feasible and of significant clinical improvement. The study will have 10% Type I error and 90% power to detect an effective treatment using a one-stage design based on the true proportion of patients achieving 3-year PFS is at least 80% versus the null hypothesis that the true complete response rate is at most 60%.

Based upon these parameters, our sample size will be 36 evaluable patients. For the final analysis, if 25 or fewer patients are alive and without progression from among all 36 evaluable patients accrued, we will consider this regimen ineffective for this patient population. If, on the other hand, 26 or more patients are alive and without progression, this will be considered sufficient evidence that this treatment may be recommended for further testing in subsequent studies, particularly in a randomized setting.

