#### **10.3.2 Secondary Objectives**

To assess toxicity, all adverse events will be summarized as to type, severity, frequency, timing and attribution. Descriptive frequencies and proportions will be used for this analysis.

To determine rates of conversion from PR to CR, only patients who had a PR at the time of registration and who complete  $\geq 1$  complete cycle of ibrutinib maintenance therapy will be evaluable for this endpoint. These rates will be calculated as a proportion together with exact 90% confidence limits.

To determine median overall survival (OS) after 4 years, Kaplan-Meier curves will be determined for overall survival and the five-year point on this curve, along with 90% confidence limits, will be determined. Patients will be evaluated monthly for the first 6 months on treatment, then every 3 months thereafter. Patients who go off treatment will continue to be followed for survival up to a maximum of 4 years post-first dose. Follow-up will occur every 3 months (up to 2 years after the first dose of treatment) and then every 6 months thereafter (up to 4 years post-first dose).

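### Median OS is a poor match for follow-up capped at 4 years: it is very unlikely to be estimable if treatment works as targeted, and may not be estimable even under the null

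*Combined protocol and SAP*

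**What the plan says.** Four places name the median as the OS summary:

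- Study Summary, secondary objectives: "Median overall survival at 4 years".
- Section 2.2.3: "Median OS after 4 years will be calculated".
- Section 6.2.3, whose title repeats the median and whose text reads: "Overall survival (OS) will be defined as the duration of time from start of treatment up to 4 years from the start of study treatment".
- Section 10.3.2: "To determine median overall survival (OS) after 4 years, Kaplan-Meier curves will be determined for overall survival". The same sentence then asks for the five-year point on that curve with 90% confidence limits.

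Sections 2.2.3, 4.7 and 10.3.2 and footnote 11 of the Section 5.0 schedule limit survival follow-up to 4 years from first dose. Section 4.7 adds only one visit, about 30 days after the last dose, for patients who complete 4 years of treatment.

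The plan gives no expected OS rate, no expected number of deaths, and no fallback if the median is not reached. Section 10.1.2 says only that OS is assessed after 4 years and mentions no median.

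**The concern.** A Kaplan-Meier median exists only if the curve falls to 50% or below while patients are still observed. Patients enter this trial already in response, and the design targets 80% 3-year PFS. More than half of them may well be alive when follow-up closes at year 4. In that case the median is reported as not reached, and the other planned summary, the five-year point, lies a year past the cap. The trial could then end with an OS curve but no estimable OS summary, and this is most likely when the treatment works.

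Section 6.2.3 also names neither the event nor a censoring rule. Section 6.1, by contrast, states the event for PFS.

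**Working it through.** **Inputs.** From Section 10.2:

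- Null: "Our null hypothesis is that ibrutinib maintenance will yield no improvement upon the 60% three-year PFS observed in" the background studies.
- Target: "We consider an observed three-year PFS of 80% both feasible and of significant clinical improvement".
- Error rates: "The study will have 10% Type I error and 90% power to detect an effective treatment using a one-stage design".
- Size: "Based upon these parameters, our sample size will be 36 evaluable patients", with success declared at 26 or more alive and progression-free.

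From Section 6.1: PFS runs from start of treatment to progression or death from any cause. Every death is therefore a PFS event, and OS cannot be shorter than PFS.

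**1. The plan's own design.** By the exact binomial with n = 36 and success at 26 or more:

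- P(X ≥ 26 | 0.60) = 0.0904
- P(X ≥ 26 | 0.80) = 0.9111

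The stated 10% and 90% reproduce as limits, and 36 is the smallest n that meets both.

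**2. Deaths needed.** With 36 patients and complete follow-up, the curve reaches 50% only with at least 36/2 = 18 deaths by year 4.

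**3. A check without a hazard model.** If 26 or more of 36 are alive and progression-free at 3 years, at most 36 − 26 = 10 have died by then. Reaching the median would need at least 18 − 10 = 8 further deaths in the single remaining year.

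**4. Bounds under a constant hazard (assumption).** S(4) = S(3)^(4/3), and median PFS = 3 × ln 0.5 / ln S(3). For example, 0.8^(4/3) = 0.743 and 0.6^(4/3) = 0.506. Because OS is at least PFS, P(median OS reached by year 4) is at most P(Bin(36, 1 − S(4)) ≥ 18).

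| 3-year PFS | 4-year PFS | Median PFS (years) | Upper bound |
|---|---|---|---|
| 80% (target) | 74.3% | 9.3 | 0.0015 |
| 70% (midway) | 62.2% | 5.8 | 0.093 |
| 60% (null) | 50.6% | 4.07 | 0.537 |

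Section 1.1 puts the historical rate at 58% to 64%. Over that range the bound runs from 0.64 (median PFS 3.8 years) to 0.32 (4.7 years).

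**5. Sensitivity.**

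- Hazard shape: Weibull shapes 0.7 to 1.5 give bounds of 0.40 to 0.76 at the null (median PFS 4.6 down to 3.7 years) and 0.0006 to 0.0065 at the target.
- Dropout of 10% to 20%, with OS set equal to PFS: about 0.47 to 0.48 at the null, below 0.002 at the target.
- All 39 patients analysed (36 plus up to 3 replaced), needing 20 deaths: 0.47 at the null, 0.0006 at the target.
- OS better than PFS at the null: if the OS hazard were 75%, 60% or 50% of the PFS hazard, the chance would be 0.146, 0.030 or 0.006. These ratios are illustrations; the documents support none of them.

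**The case against.** The strongest reply has four parts.

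**Not reached is a legitimate result.** OS here is descriptive, with no test or decision attached, and Section 10.3.2 plans a Kaplan-Meier curve in any case. A reader might infer that the survival objective would go wholly unanswered. The documents do not support that, because the curve will exist. What remains is that neither planned numerical summary of it, the median or the five-year point, need be estimable.

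**The null does not make the median unreachable.** A reader might infer that the median will almost never be reached whatever the truth. That does not follow at 60%. The constant-hazard median PFS exceeds the cap by only 0.07 years, a hazard rising as Weibull shape 1.3 brings it to 3.8 years, and the bound is 54%. Section 1.1 describes prognosis after progression as dismal, which points towards the bound rather than away from it. This part stands in full.

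**Section 6.2.3 will be read sensibly.** Taken literally, its definition could give every survivor an OS of 4 years and produce a spurious median of 4.0. That reading is strained. The term overall survival and the Kaplan-Meier method both imply death as the event, and the 4-year limit reads naturally as administrative censoring. The omission is a drafting gap and is unlikely to lead to a wrong result.

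**Correcting the five-year point would do most of the work.** This is largely true of Section 10.3.2, but the median would remain the named summary in all four places.

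**Conclusion.** The point holds as a mismatch between the chosen summary and the length of follow-up. At the design target the median is very unlikely to be estimable: at most 0.15% under a constant hazard and at most 0.65% across the Weibull shapes tried. At 70% 3-year PFS the bound is about 9%. At the 60% null it may or may not be estimable: the bound is 54%, or 40% to 76% across the same shapes.

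These are upper limits that would be attained only if every PFS event were a death. They assume 36 patients and complete follow-up. Without an OS rate in the documents, the actual chance below them cannot be stated. No type I error, power or treatment decision is affected. The change is worth making because it is cheap and the affected endpoint is secondary but named throughout the plan.

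**What to change.** 1. In the Study Summary, 2.2.3, 6.2.3 and 10.3.2, make the OS summary the Kaplan-Meier estimate of the 4-year OS rate with 90% confidence limits. In 10.3.2 this replaces the five-year point. Report the median only if the curve reaches 50% within follow-up.

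2. As a minor clarification in 6.2.3, state that OS runs from first dose to death from any cause, and that patients not known to have died are censored at the date last known alive, at most 4 years after first dose.

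3. Reconcile footnote 11 of Section 5.0, which schedules off-treatment follow-up until progression, with Sections 2.2.3 and 4.7 (survival follow-up to 4 years) and 7.2.5 (which refers to follow-up for OS after progression). The 4-year OS rate needs survival status after progression.

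The replacement is estimable within the cap. By the normal approximation, the 90% half-width is 1.645 × √(S(1 − S)/36): about 12 percentage points at S = 0.74 and about 14 at S = 0.51.

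The cost is wording in four places plus the follow-up reconciliation, with no added patients or visits. If any site has stopped contact at progression under footnote 11, survival status for those patients would have to be recovered.

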### 2.3 Exploratory Objectives & Endpoints

Compare MRD results overtime by PCR and correlate these with PFS and OS.

We will obtain archived tissue (FFPE slides) from a previous biopsy from all patients for baseline clone identification; in addition, we will collect peripheral whole blood samples at baseline, 1 month after first dose, 6 months after first dose, and approximately 18-24 months after first dose. MRD analysis will be

Study Numbers: NU 14H06  
PCI-32765MCL2003Initial version: September 24, 2014  
AMD 11: ver. date 08.06.2022

conducted using PCR methods and results will be compared over time and correlated with PFS and OS.

### 3.0 SELECTION OF SUBJECTS

The target population for this phase II study is patients with histologically confirmed (previously untreated) mantle cell lymphoma (MCL) who have achieved response (CR or PR) to intensive induction systemic chemotherapy (with or without ASCT). This will be a multicenter trial conducted at Northwestern University. Northwestern University will serve as the lead site and coordinating center for this study. Participating sites will include University of Utah, and Dana Farber d/b/a Massachusetts General Hospital.

A total of 36 *evaluable* subjects will be needed for this trial (defined as having received  $\geq$  1 complete cycle of treatment). Approximately 5 potentially eligible patients are seen per month, and it is anticipated that at least 2 per month will be accrued *once the protocol is open and enrolling at all sites*. Potential patients may be referred to the Principal Investigator (PI) at Northwestern University or to the local PI at each participating site.

Eligibility will be evaluated by the study team according to the following criteria. Eligibility waivers are not permitted. Subjects must meet all of the inclusion and exclusion criteria to be registered to the study. Study treatment may not begin until a subject is registered. Please refer to Section 11.4 for complete instructions regarding registration procedures.

